**Knee Society Score**

The Knee Society Score is an investigator-completed questionnaire that is used to objectively measure a patient's ability to function before and after total knee arthroplasty (Insall 1989). If possible, the assessment should be completed by the same person throughout the study.

**Harris Hip Score**

The Harris Hip Score is an investigator-completed questionnaire that is used to objectively measure a patient's ability to function before and after total hip arthroplasty (Harris 1969). If possible, the assessment should be completed by the same person throughout the study.

**8.2.3.11. Laboratory Testing**

The central laboratory will analyze all screening and on-study laboratory samples for blood chemistry, hematology, HbA1c, urine analysis, urine drug tests and serum pregnancy tests. Urine pregnancy and ESR testing will be done at the site using kits provided by the central laboratory.

Regeneron or its designee will be responsible for fasinumab PK, anti-fasinumab antibody, biomarker assessments, and pharmacogenetic sample assessments; the central laboratory will ship the samples to Regeneron or a specialty laboratory depending on the assessment.

All samples will be collected before SC study drug administration. Missed tests should be reported in the source documents and in the eCRF, as appropriate. Central laboratory kits will be provided for sample collection and shipment. Detailed instructions for blood sample collection are in the laboratory manual provided to study sites.

Samples for laboratory testing will be collected at visits according to [Table 1](#). Tests will include:

**Blood Chemistry**

Sodium	Total protein, serum	Total bilirubin
Potassium	Creatinine	Phosphorus
Chloride	Blood urea nitrogen	Uric acid
Carbon dioxide	Aspartate aminotransferase (AST)	Creatine phosphokinase
Calcium	Alanine aminotransferase (ALT)	
Glucose	Alkaline phosphatase	
Albumin	Lactate dehydrogenase	

**Hematology**

Hemoglobin	Differential:
Hematocrit	Neutrophils
Red blood cells (RBCs)	Lymphocytes
White blood cells (WBCs)	Monocytes
Red cell indices	Basophils
Platelet count	Eosinophils

**Urinalysis**

Color	Glucose	RBC
Clarity	Blood	Hyaline and other casts
pH	Bilirubin	Bacteria
Specific gravity	Leukocyte esterase	Epithelial cells
Ketones	Nitrite	Crystals
Protein	WBC	Yeast

**Urine Electrolytes**

Creatinine  
Phosphorus

**Other Laboratory Tests**

Serum and urine samples for pregnancy testing will be collected from women of childbearing potential (as defined in Section 8.2.1.6) at time points according to Table 1. At each study visit during the treatment period, urine pregnancy testing will be done before the study drug is administered. In the event of a positive urine pregnancy test result, the patient should have a serum pregnancy test with a negative result in order to continue study participation. If the serum pregnancy test is positive, the patient should be withdrawn from study drug and should be asked to return to the clinic for all remaining study visits per the visit schedule (see Table 1).

To assess postmenopausal status for women  $\leq 59$  years of age, serum samples to test for FSH levels and estradiol levels will be collected for analysis at the central laboratory according to Section 8.2.1.6.

Samples will be collected for HbA1c and ESR testing at time points according to Table 1.

Urine drug testing will be performed at screening and includes amphetamines/methamphetamines, barbiturates, benzodiazepines, cannabinoids, cocaine, and opiates.

Blood samples for fasinumab PK and ADA assessment (Section 8.2.4) will also be collected.

**Abnormal Laboratory Values and Laboratory Adverse Events**

- All laboratory values must be reviewed by the investigator or authorized designee.
- Significantly abnormal tests must be repeated to confirm the nature and degree of the abnormality. When necessary, appropriate ancillary investigations should be initiated. If the abnormality fails to resolve or cannot be explained by events or conditions unrelated to the study medication or its administration, the medical monitor must be consulted.
- The clinical significance of an abnormal test value, within the context of the disease under study, must be determined by the investigator.

Criteria for reporting laboratory values as an AE are provided in Section 9.4.5.

**8.2.3.12. Injection Site Evaluations**

An injection site evaluation should be conducted following the injection at each dosing visit, according to Table 1.

## **8.2.4. Pharmacokinetic and Anti-Drug Antibody Procedures**

### **8.2.4.1. Drug Concentration Measurements and Samples**

Samples for fasinumab concentration will be collected at time points listed in [Table 1](#). Detailed instructions for blood sample collection are included in the laboratory manual provided to study sites.

Any unused samples may be used for exploratory biomarker research.

### **8.2.4.2. Anti-Drug Antibody Measurements and Samples**

Samples for ADA assessment will be collected at time points listed in [Table 1](#). Detailed instructions for blood sample collection are included in the laboratory manual provided to study sites.

Any unused samples may be used for exploratory biomarker research.

## **8.2.5. Research Samples**

### **8.2.5.1. Biomarkers**

Serum and plasma samples will be collected at time points according to [Table 1](#). These samples may be used to measure biomarkers related to inflammation, collagen and bone turnover, OA pain and NGF and may include CTX-I, osteocalcin, hs-CRP, and matrix metalloprotein generated collagen fragments (CIM, C3M). Samples may be used to study other markers of collagen and bone turnover, OA and pain. If necessary, samples may also be used to identify markers associated with adverse events.

### **8.2.5.2. Future Biomedical Research**

Unused research samples, as well as unused PK and ADA samples, will be stored for up to 15 years after the final date of the database lock. The unused samples may be utilized for future biomedical research of OA and other diseases. No additional samples will be collected for future biomedical research. After 15 years, any remaining samples will be destroyed.

## **8.2.6. Genomics Sub-study – Optional**

Patients who agree to participate in the genomics sub-study will be required to sign a separate genomics sub-study ICF before collection of the samples. Patients are not required to participate in the genomics sub-study in order to enroll in the primary study. Samples for DNA extraction should be collected on day 1/baseline (predose), but may be collected at any study visit.

DNA samples for the genomics sub-study will be de-identified as defined by the International Council for Harmonisation (ICH) guideline E15. Sub-study samples will be stored for up to 15 years after the final date of the database lock and may be used for research purposes. The purpose of the genomic analyses is to identify genomic associations with collagen and bone turnover, OA, pain, and response to fasinumab. In addition, associations between genomic variants and prognosis or progression of OA as well as other diseases may also be studied. These data may be used or combined with data collected from other studies to identify and validate genomic markers related to the study drug or other diseases. Analyses may include sequence

determination or single nucleotide polymorphism studies of candidate genes and surrounding genomic regions. Other methods, including whole-exome sequencing, whole-genome sequencing, and DNA copy number variation may also be performed. The list of methods may be expanded to include novel methodology that may be developed during the course of this study or sample storage period.

## **9. SAFETY DEFINITIONS, REPORTING, AND MONITORING**

### **9.1. Obligations of Investigator**

The investigator must promptly report to the IRB/EC all unanticipated problems involving risks to patient. This includes death from any cause and all SAEs related to the use of the study drug. It is recommended that all SAEs be reported to the IRB/EC, regardless of assessed causality.

### **9.2. Obligations of Sponsor**

During the course of the study, the sponsor will report in an expedited manner all SAEs that are both unexpected and at least reasonably related to the study drug (SUSAR), to the health authorities, IRBs/ECs as appropriate, and to the investigators.

Any AE not listed as an expected event in the Investigator's Brochure or in this protocol will be considered as unexpected. Any worsening of or new onset of symptoms related to OA, which occur during the screening/washout period prior to study drug administration will be considered expected.

In addition, the sponsor will report in an expedited manner all SAEs that are expected and at least reasonably related to the study drug to the health authorities, according to local regulations.

At the completion of the study, the sponsor will report all safety observations made during the conduct of the trial in the clinical study report to health authorities and IRBs/ECs as appropriate.

### **9.3. Definitions**

#### **9.3.1. Adverse Event**

An AE is any untoward medical occurrence in a patient administered a study drug which may or may not have a causal relationship with the study drug. Therefore, an AE is any unfavorable and unintended sign (including abnormal laboratory finding), symptom, or disease which is temporally associated with the use of a study drug, whether or not considered related to the study drug.

An AE also includes any worsening (ie, any clinically significant change in frequency and/or intensity) of a pre-existing condition that is temporally associated with the use of the study drug.

#### **9.3.2. Serious Adverse Event**

An SAE is any untoward medical occurrence that at any dose:

- Results in **death** – includes all deaths, even those that appear to be completely unrelated to study drug (eg, a car accident in which a patient is a passenger).

- Is **life-threatening** – in the view of the investigator, the patient is at immediate risk of death at the time of the event. This does not include an AE that had it occurred in a more severe form, might have caused death.
- Requires in-patient **hospitalization** or **prolongation of existing hospitalization**. In-patient hospitalization is defined as admission to a hospital or an emergency room for longer than 24 hours. Prolongation of existing hospitalization is defined as a hospital stay that is longer than was originally anticipated for the event, or is prolonged due to the development of a new AE as determined by the investigator or treating physician.
- Results in persistent or significant **disability/incapacity** (substantial disruption of one's ability to conduct normal life functions).
- Is a **congenital anomaly/birth defect**
- Is an **important medical event** - Important medical events may not be immediately life-threatening or result in death or hospitalization, but may jeopardize the patient or may require intervention to prevent one of the other serious outcomes listed above. Examples of these include intensive treatment in an emergency room or at home for allergic bronchospasm; blood dyscrasias or convulsions that do not result in hospitalization; or development of drug dependency or drug abuse.

### 9.3.3. Adverse Events of Special Interest

An AESI (serious or non-serious) is one of scientific and medical concern specific to the sponsor's product or program, for which ongoing monitoring and rapid communication by the investigator to the sponsor can be appropriate. Such an event might warrant further investigation in order to characterize and understand it. Depending on the nature of the event, rapid communication by the trial sponsor to other parties (eg, regulators) might also be warranted (Section 9.4.3).

Adverse events of special interest are described in Section 9.4.3.

## 9.4. Recording and Reporting Adverse Events

### 9.4.1. Adverse Events

The investigator (or designee) will record all AEs that occur from the time the informed consent is signed until the end of the follow-up period (week 44). Refer to the study reference manual for the procedures to be followed.

Information on follow-up for AEs is provided in Section 9.4.6. Laboratory, vital signs, or ECG abnormalities are to be recorded as AEs as outlined in Section 9.4.5.

### 9.4.2. Serious Adverse Events

All SAEs, regardless of assessment of causal relationship to study drug, must be reported to the sponsor (or designee) within 24 hours. Refer to the study reference manual for the procedure to be followed.

Information not available at the time of the initial report must be documented in a follow-up report. Substantiating data such as relevant hospital or medical records and diagnostic test reports may also be requested.

In the event the investigator is informed of an SAE after the patient completes the follow-up period (week 44)/early termination visit, the following will apply:

- SAE with an onset within 30 days of the end of the follow-up period (week 44)/early termination visit - the SAE will be reported to the sponsor. The investigator should make every effort to obtain follow-up information on the outcome until the event is considered chronic and/or stable.
- SAE with an onset day greater than 30 days from the end of the follow-up period (week 44)/early termination visit - only SAEs deemed by the investigator to be drug-related will be reported to the sponsor. The investigator should make every effort to obtain follow-up information on the outcome of a drug-related SAE until the event is considered chronic and/or stable.
- SAE reported by the patient at the end of study phone call and deemed by the investigator to be drug-related will be reported to the sponsor. The investigator should make every effort to obtain follow-up information on the outcome of a drug-related SAE until the event is considered chronic and/or stable.

### 9.4.3. Other Events that Require Accelerated Reporting to Sponsor

The following events also require reporting to the sponsor (or designee) within 24 hours of learning of the event:

**Symptomatic Overdose of Study Drug:** Accidental or intentional overdose of at least 2 times the intended dose of study drug within the intended therapeutic window, if associated with an AE

**Pregnancy:** Although pregnancy is not considered an AE, it is the responsibility of the investigator to report to the sponsor (or designee), within 24 hours of identification, any pregnancy occurring in a female during the study or within 20 weeks of the last dose of study drug. Any complication of pregnancy affecting a female study patient and/or fetus and/or newborn that meets the SAE criteria must be reported as an SAE. Outcome for all pregnancies should be reported to the sponsor.

**Adverse Events of Special Interest:** All AESI, serious and non-serious, must be reported within 24 hours of identification using the same reporting process as for SAE reporting, per Section 9.4.2. Monitoring of AESIs is described in Section 9.6.1. Adverse events of special interest for this study are:

- Adjudicated arthropathy (as confirmed by adjudication)

- Joint replacement surgery (refer to Section 9.6.1.4 for when to report as an AESI)
- Sympathetic nervous system dysfunction (as diagnosed after consultation with an appropriate specialist, such as a neurologist and/or cardiologist)
- Peripheral sensory AEs that require a neurology or other specialty consultation

Refer to the study manual for the procedures to be followed.

#### **9.4.4. Reporting Adverse Events Leading to Withdrawal from the Study**

All AEs that lead to a patient's withdrawal from the study must be reported to the sponsor's medical monitor within 30 days.

Refer to the study reference manual for the procedures to be followed.

#### **9.4.5. Abnormal Laboratory, Vital Signs, or Electrocardiogram Results**

The criteria for determining whether an abnormal objective test finding should be reported as an AE include:

- the test result is associated with accompanying symptoms, and/or
- the test result requires additional diagnostic testing or medical/surgical intervention, and/or
- the test result leads to a change in dosing (outside of protocol-stipulated dose adjustments), discontinuation from the study, significant additional concomitant drug treatment, or other therapy

Contact the medical monitor in the event the investigator feels that an abnormal test finding should be reported as an AE, although it does not meet any of the above criteria.

Repeating an abnormal test, in the absence of any of the above conditions, does not constitute an AE. Any abnormal test result that is determined to be an error does not require reporting as an AE.

Evaluation of severity of laboratory abnormalities will be assessed according to the scale outlined in Section 9.5.1.

#### **9.4.6. Follow-up**

Adverse event information will be collected until the patient's last study visit.

Serious adverse event information will be collected until the event is considered chronic and/or stable.

### **9.5. Evaluation of Severity and Causality**

#### **9.5.1. Evaluation of Severity**

The severity of AEs will be graded according to the following scale:

- **Mild:** Does not interfere in a significant manner with the patient's normal functioning level. It may be an annoyance. Prescription drugs are not ordinarily needed for relief of symptoms, but may be given because of personality of the patient.
- **Moderate:** Produces some impairment of functioning but is not hazardous to health. It is uncomfortable or an embarrassment. Treatment for symptom may be needed.
- **Severe:** Produces significant impairment of functioning or incapacitation and is a definite hazard to the patient's health. Treatment for symptom may be given and/or patient hospitalized.

If a laboratory value is considered an AE, its severity should be based on the degree of physiological impairment the value indicates.

### **Injection Site Reactions**

The severity of injection site reactions will be graded according to the following scale (semi-colon indicates "or" within description of grade):

- **Mild:** Pain that does not interfere with activity; mild discomfort to touch;  $\leq 5$  cm of erythema or induration that does not interfere with activity
- **Moderate:** Pain that requires repeated use of non-narcotic pain reliever  $>24$  hours or interferes with activity; discomfort with movement; 5.1 cm to 10 cm erythema or induration or induration that interferes with activity
- **Severe:** Pain that requires any use of narcotic pain reliever or that prevents daily activity; significant discomfort at rest;  $>10$  cm erythema or induration; prevents daily activity; requires emergency room visit or hospitalization; necrosis or exfoliative dermatitis

### **9.5.2. Evaluation of Causality**

#### **Relationship of Adverse Events to Study Drug:**

The relationship of AEs to study drug will be assessed by the "blinded" investigator, and will be a clinical decision based on all available information. The following question will be addressed:

Is there a reasonable possibility that the AE may have been caused by the study drug?

The possible answers are:

**Not Related:** There is no reasonable possibility that the event may have been caused by the study drug

**Related:** There is a reasonable possibility that the event may have been caused by the study drug

The investigator should justify the causality assessment of each SAE.

A list of factors to consider when assessing the relationship of AEs to study drug is provided below. Please note that this list is not exhaustive.

Is there a reasonable possibility that the event may have been caused by the study drug?

No:

- due to external causes such as environmental factors or other treatment(s) being administered
- due to the patient's disease state or clinical condition
- do not follow a reasonable temporal sequence following the time of administration of the dose of study drug
- do not reappear or worsen when dosing with study drug is resumed

Yes:

- could not be explained by environmental factors or other treatment(s) being administered
- could not be explained by the patient's disease state or clinical condition
- follow a reasonable temporal sequence following the time of administration of the dose of study drug
- resolve or improve after discontinuation of study drug
- reappear or worsen when dosing with study drug
- are known or suspected to be a response to the study drug based upon preclinical data or prior clinical data

#### **Relationship of Adverse Events to Study Conduct**

The relationship of AEs to study conduct will be assessed by the "blinded" investigator, and will be a clinical decision based on all available information. The following question will be addressed:

Is there a reasonable possibility that the AE may have been caused by study conduct?

The possible answers are:

**Not Related:** There is no reasonable possibility that the event may have been caused by study conduct.

**Related:** There is a reasonable possibility that the event may have been caused by study conduct.

The investigator should justify the causality assessment of each SAE.

A list of factors to consider when assessing the relationship of AEs to study conduct is provided below. Please note that the list is not exhaustive.

Is there a reasonable possibility that the event may have been caused by the study conduct?

Is there a reasonable possibility that the event may have been caused by the study conduct?

No:

- due to external causes such as environmental factors or other treatment(s) being administered
- due to the patient's disease state or clinical condition
- do not follow a reasonable temporal sequence following the course of the study

- do not reappear or worsen when dosing with study participation is resumed

Yes:

- could not be explained by environmental factors or other treatment(s) being administered
- could not be explained by the patient's disease state or clinical condition
- follow a reasonable temporal sequence following the course of the study
- resolve or improve after discontinuation from study participation.
- reappear or worsen when study participation is resumed

## 9.6. Safety Monitoring

The investigator will monitor the safety of study patient at his/her site(s) as per the requirements of this protocol and consistent with current Good Clinical Practice (GCP). Any questions or concerns should be discussed with the sponsor in a timely fashion. The sponsor will monitor the safety data from across all study sites. The medical monitor will have primary responsibility for the emerging safety profile of the compound, but will be supported by other departments (eg, Pharmacovigilance and Risk Management; Biostatistics and Data Management). Safety monitoring will be performed on an ongoing basis (eg, individual review of SAEs) and on a periodic cumulative aggregate basis.

### 9.6.1. Monitoring Adverse Events of Special Interest

#### 9.6.1.1. Adjudicated Arthropathy

Adjudicated arthropathy is an umbrella term that encompasses the following conditions:

- Rapidly progressive OA type 1 and 2
- Subchondral insufficiency fractures
- Primary osteonecrosis

In addition, AAs will be evaluated to determine if they meet the criteria for destructive arthropathy.

Potential events of AA will be monitored via clinical signs and symptoms of worsening joint pain during the course of the study (eg, by applying adverse experiences, the joint pain questionnaire and imaging) as well as scheduled imaging and pre-operative imaging, if a patient requires a joint replacement during the study.

Clinically significant worsening of joint pain during the course of this study is defined as a worsening of pain in any joint that occurs in spite of treatment with analgesics, is in the opinion of the investigator inconsistent with the normal fluctuation of pain or progression of OA, and is at least 2 weeks duration (or less than 2 weeks if deemed clinically significant at the discretion of the investigator).

If a patient reports an increase in pain as described above, study drug administration will be withheld while imaging of the affected joint, as well as any additional imaging deemed appropriate to understand the cause of the worsening pain, is performed (Section 8.2.3.7). A decision to

perform imaging after patient reported worsening of joint pain will be documented in the respective case report form (CRF) page. Images, along with any other radiographic evaluation, will be submitted to the Adjudication Committee for review (Section 5.3.2). The investigator may consider aspiration of synovial fluid for further analysis such as cell count and crystal analysis.

If routine imaging suggests the presence of one of the types of AA, study drug administration will be withheld. Any additional imaging deemed appropriate will be obtained. The images, along with results of any other radiographic evaluation, will be submitted to the Adjudication Committee for review (Section 5.3.2).

If the adjudication does not confirm the presence of AA, according to the adjudication criteria, study drug may be restarted.

Study drug dosing will be permanently discontinued for patients with findings that suggest AA; the patients will be referred for orthopedic consultation. If presence of AA is confirmed by the Adjudication Committee, the case must be reported as an AESI (Section 9.3.3, Section 9.4.3).

Any patient whose study drug is discontinued due to an AA should be encouraged to return to the clinic for all remaining study visits. Prior to the scheduled JR, the patient should complete the pre-operative study visit and, after the JR, should complete the week 4 and week 20 post-operative study visits (Section 8.2.3.10, Table 2). Pre-operative images, along with any other radiographic evaluation will be submitted to the Adjudication Committee for review (Section 5.3.2).

Details of data collection for adjudication of events will be provided in the adjudication charter.

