Data from studies of tanezumab and fulranumab demonstrated these molecules were associated with an increased risk of destructive arthropathy (DA), a unique clinical form of rapidly progressive arthropathy over and above that seen in the normal progression of osteoarthritis. Analyses of the tanezumab data by its sponsor, defined by anatomic pathological criteria on specimens obtained on joint replacement (JR), revealed that the risk of DA increases with tanezumab dose and is further increased with the concomitant use of chronic NSAIDs (>90 days) (Lane 2010). Most cases of DA occurred in joints with a documented history of OA.

Based on the potential risk of DA identified in tanezumab and fulranumab, the United States (US) Food and Drug Administration (FDA) placed this class of anti-NGF antibodies on clinical hold in 2010. Following a review of anti-NGF antibody clinical data in March 2012, the FDA determined that clinical studies of anti-NGF therapies could resume if mitigation strategies are implemented to minimize the risk of DA. To address concerns about potential events of DA, a risk-mitigation approach is also being implemented for all fasinumab studies, as outlined in Section 9.6.1.1. This approach includes sensitive, prospective, and rigorous radiologic screening for select changes in joint structure. The patients who develop these changes, which are referred to throughout this document as adjudicated arthropathy (AA), are required to discontinue study therapy.

Since the removal of the FDA clinical hold, Regeneron has conducted or initiated several clinical trials of fasinumab. In all clinical studies to date, fasinumab was associated with a low rate of discontinuations due to adverse events. Patients treated with fasinumab generally had more frequent events than did placebo-treated patients of arthralgia, joint swelling, peripheral edema, altered peripheral sensation (eg, paresthesia, dysesthesia), and myalgia.

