#### **7.3.2.2. Reasons for Temporary Discontinuation of Study Drug**

Study drug may be temporarily discontinued due to medical need, as determined by the investigator. Subcutaneous study drug (fasinumab or fasinumab-matching placebo) will be temporarily withheld while awaiting imaging adjudication for worsening joint pain or when routine imaging suggests adjudicated arthropathy and prompts the need for additional imaging (see Section 9.6.1.1), or for patients who are determined to have orthostatic hypotension or determined to have new or worsening symptoms suggestive of sympathetic nervous system dysfunction while awaiting evaluation by a specialist (see Section 9.6.1.2). Patients may continue to take NSAID or NSAID-matching placebo during this time. Subcutaneous study drug (fasinumab or fasinumab-matching placebo) should not be re-started until the next study visit unless imaging/evaluation results are available within the current visit window. If oral study drug is temporarily discontinued by the investigator, patients may continue to take SC study drug during this time.

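### Protocol 9.6.1.1 makes findings that merely suggest adjudicated arthropathy a permanent stop, although the same section and 7.3.2.2 make them a temporary hold

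*Protocol*

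**What the plan says.** Protocol 9.6.1.1 sets out a sequence. For scheduled imaging: "If routine imaging suggests the presence of one of the types of AA, study drug administration will be withheld". The images go to the Adjudication Committee, and then: "If the adjudication does not confirm the presence of AA, according to the adjudication criteria, study drug may be restarted".

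The next paragraph opens: "Study drug dosing will be permanently discontinued for patients with findings that suggest AA". It adds orthopedic referral and continues: "If presence of AA is confirmed by the Adjudication Committee, the case must be reported as an AESI".

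Protocol 7.3.2.2 covers temporary discontinuation. SC study drug "will be temporarily withheld while awaiting imaging adjudication for worsening joint pain or when routine imaging suggests adjudicated arthropathy", and it "should not be re-started until the next study visit unless imaging/evaluation results are available within the current visit window". On the oral drug it says: "Patients may continue to take NSAID or NSAID-matching placebo during this time".

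Four other places bear on the intended rule:
- Section 1: "The patients who develop these changes, which are referred to throughout this document as adjudicated arthropathy (AA), are required to discontinue study therapy".
- Section 7.3.2.1 lists AA, as an adverse event of special interest (AESI), among the reasons for a permanent stop, and refers to 9.6.1.1 for the description. Section 7.3.2 refers there too.
- Section 9.4.3 defines that AESI as AA confirmed by adjudication.
- Section 7.1 defines study drug as both the SC and the oral product.

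**The concern.** A patient whose imaging suggests AA but whose adjudication is negative may restart under one paragraph of 9.6.1.1 and must stop for good under the next. The sentence on committee confirmation does not settle this, because it attaches confirmation only to AESI reporting. Read on its own, it leaves room for a permanent stop that does not wait for the committee.

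This is a dosing instruction for the programme's main joint-safety risk, and the general discontinuation sections send sites to it. Two sites could handle the same case differently: one resumes treatment after a negative adjudication, the other ends it. At stake are consistent patient management and study treatment for patients who turn out not to have AA.

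**Working it through.** No figure in the plan depends on this rule, so the check is a comparison of texts. Take a patient whose imaging suggests AA and follow each rule.

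| Adjudication status | Hold-and-restart text (9.6.1.1, 7.3.2.2) | Permanent-stop sentence in 9.6.1.1, read literally | 7.3.2.1 with 9.4.3 |
|---|---|---|---|
| Pending | Hold | Permanent stop | No AA stop yet |
| Confirmed | No restart permission | Permanent stop | Permanent stop |
| Not confirmed | May restart | Permanent stop | No AA stop |
| Indeterminate | Not addressed; literally not confirmed, so may restart | Permanent stop | No AA stop |

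The rules agree only in the confirmed row. Taken literally, the permanent-stop sentence leaves the restart provision with no effect for imaging-suggested cases.

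**Which trigger is intended.** No sentence states it outright, but the evidence points one way:
1. Section 7.3.2.1 makes the AESI of AA the reason to stop, and 9.4.3 requires adjudication for that AESI.
2. Section 1 ties the requirement to stop to patients who develop AA.
3. Section 7.3.2.2 holds SC drug while adjudication is awaited, which would be pointless if the stop were already permanent.
4. Section 9.6.1.2 has the parallel pattern for sympathetic nervous system dysfunction: hold, evaluate, and stop for good only if the specialist finds it. It also uses *suggest* for the specialist's final conclusion, so the word is not reserved for unconfirmed suspicion.

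**What the size depends on.** Table 1 places SC doses at weeks 0, 4, 8, 12, 16 and 20. For a trigger at week w, before that visit's dose, let G be the number of doses at week w or later:
- w = 2 or 4: G = 5 (weeks 4, 8, 12, 16, 20).
- w = 16: G = 2 (weeks 16, 20), or 1 if the X-ray is read after the week 16 dose.
- w = 24 or 44: G = 0.

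Doses missed during a proper hold would be lost anyway. If k doses are missed while waiting, the net loss due to the wording is G − min(k, G). The documents do not give the adjudication time, so k is an assumption:
- G = 5: net loss is 5, 4, 3, 2, 1, 0 for k = 0 to 5.
- G = 2: net loss is 2, 1, 0 for k = 0 to 2.
- G = 1: net loss is 1 or 0.

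Every case reaches zero within the range. Oral drug may continue during the hold under 7.3.2.2, whereas a literal permanent stop of study drug would end it. That is up to 24 − 16 = 8 weeks after a week 16 trigger, or 24 − 4 = 20 weeks after a week 4 trigger. The number of patients with suggestive imaging and a negative adjudication is not in the documents, so no total follows.

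**SC or oral.** The holds in 9.6.1.1 and 9.6.1.2 refer to study drug, which 7.1 defines as both products. Section 7.3.2.2 withholds only the SC drug for the same events.

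**The case against.** The strongest defence is that the section resolves itself when read in order. Imaging raises suspicion, drug is held, the committee reviews, a negative result permits restart, and the permanent-stop sentence is then the remaining branch. This supports confirmed AA as the intended trigger. It does not remove the contradiction, because the following sentence speaks as though confirmation were still open and links it only to AESI reporting.

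Several limiting points stand. Restart is optional, 9.6 directs questions to the sponsor, and only patients with suggestive findings and no confirmation are exposed. Worsening pain alone calls for a hold and does not in itself meet the permanent-stop wording. On the SC and oral mismatch, 7.3.2.2 is the more specific rule and cross-refers to both AESI sections, so that edit is secondary.

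A reader might infer the opposite: that the sponsor deliberately chose a wider, precautionary stop on suspicion alone. The documents do not support this, since it would empty both the restart provision and the temporary hold for imaging-suggested cases.

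A caution about the remedy also stands. If confirmation simply replaces suspicion, an indeterminate adjudication could be read as not confirmed and hence as permission to restart. The fix has to close that gap.

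**Conclusion.** The sentence is wrong as written and should be corrected. It is a wording error in an operative rule, not a flawed design choice. That the intended trigger is adjudication-confirmed AA is an inference, though a strong one.

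The consequence is possible inconsistency between sites and possible loss of remaining doses in patients without AA. Its size cannot be determined: the schedule sets ceilings, but the net loss depends on an adjudication time that is not given, and the number of patients affected is unknown.

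Two stronger conclusions are tempting and unsupported. One is that the wording endangers joints; in fact the literal reading stops drug sooner, which is conservative for joint safety. The other is that it biases the primary result. A route exists, because Protocol 10.4.3.1 and SAP 5.7.1 leave data after treatment discontinuation out of the primary analysis and centre imputed values at the baseline mean for stops due to adverse events. Without a rate of unconfirmed cases, however, no effect on the primary result is shown, and no stated sample size or power figure changes.

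**What to change.** 1. In the permanent-stop sentence of Protocol 9.6.1.1, make the trigger AA confirmed by the Adjudication Committee.
2. In the same place, state that SC drug stays on hold until adjudication is resolved, so that an indeterminate result is not clearance to restart. The investigator's medical-need stop in 7.3.2.1 stays as it is.
3. As a secondary consistency edit, write SC study drug for the temporary holds, and the restarts that follow them, in both 9.6.1.1 and 9.6.1.2. Changing only the first would leave the two AESI sections inconsistent with each other. The permanent stop needs no such edit, because 7.1 already defines study drug as both products.

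The cost is one phrase, one added sentence, a repeated one-word edit and a clarification letter to sites. No new procedures or data are needed, and suspected cases remain on hold.
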